### 7.1 Analysis Datasets

For the Demography, Safety and Tolerability analysis, the study data tabulation model (SDTM) datasets after soft-lock of the clinical database will be used. The soft-lock of the clinical database is described by the study data management plan (DMP). Analysis datasets will be generated during the analysis according to the ICH E3, E9, and Clinical Data Interchange Standards Consortium (CDISC) Analysis Dataset Model (ADaM) guidelines.

For the EBA analysis, an EBA analysis dataset will be generated from the SDTM datasets according to the RESP30X-EBA Data Definition Table (DDT). The RESP30X-EBA DDT is a separate document that details the data specifications of the EBA analysis dataset and will be finalised prior to the first EBA analysis. In general, the EBA DDT will compromise at least the following variable:

RESP30X-EBA: Statistical Analysis Plan22 JUL 2024

| CDSIC DOMAIN  | Variable         | Label  | Type/Format   | Length |
|---------------|------------------|--|---------------|--------|
| ALL           | #REF             | Consecutive record number.   | Numeric       | LONG   |
| ALL           | STUD             | Protocol number. Insert protocol number.                                     | Character     | 200    |
| DS            | UID              | SUBJECT (RANDOMIZATION NUMBER).  | Character     | 200    |
| ALL           | ID               | ID for NONMEM dataset  | Numeric       | LONG   |
| ALL           | TIME             | Nominal sample production day  | Numeric       | LONG   |
| LB MICRO      | DVCFU            | Dependent variable   | Demical/Float | 5.2    |
| LB MICRO      | DVTTP            | Dependent variable   | Numeric       | LONG   |
| LB MICRO      | SSCFU            | Sample status for CFU counts   | Numeric       | LONG   |
| LB MICRO      | SSTTP            | Sample status for TTP counts   | Numeric       | LONG   |
| LB MICRO      | REP              | Replicate number   | Numeric       | LONG   |
| DS            | GROUP            | Group  | Numeric       | LONG   |
| DS            | TRT              | Treatment  | Numeric       | LONG   |
| DS            | REGI             | Regimen  | Character     | 200    |
| VS            | BMI              | BMI  | Demical/Float | 5.1    |
| VS            | HT               | Height   | Numeric       | LONG   |
| DM            | ETHNICITY        | Ethnicity  | Numeric       | LONG   |
| VS            | WT               | Weight   | Demical/Float | 5.1    |
| DM            | AGE              | Age  | Numeric       | LONG   |
| DM            | SEX              | Sex  | Numeric       | LONG   |
| LB MICRO      | BBLCFU           | Baseline bacterial load. (average log10 CFU on days -2 and -1)               | Numeric       | LONG   |
| LB MICRO      | BBLTTP           | Baseline bacterial load. (average TTP on days -2 and -1)                     | Numeric       | LONG   |
| LB SAFETY     | HIV              | HIV  | Numeric       | LONG   |
| CX            | EXTENT           | Severity or extent of disease  | Character     | 200    |
| CX            | CAV              | Presence of cavitation   | Numeric       | LONG   |
| LB MICRO      | SQUAL            | Sputum quality   | Numeric       | LONG   |
| LB MICRO      | SVOL             | Sputum volume  | Numeric       | LONG   |
| LB MICRO      | COMMENT          | Comments from the Microbiology Laboratory associated with sample observation | Character     | 200    |
| SU            | SMOKING          | Smoking  | Character     | 200    |
| LB MICRO      | MBGENMTBULTRA    | Genexpert MTB/RIF ULTRA Detection.   | Numeric       | LONG   |
| LB MICRO      | MBGENMTBULTRAPos | Genexpert MTB/RIF ULTRA Detection Positivity.                                | Numeric       | LONG   |
| LB MICRO      | MBGENMTBULTRACYC | Genexpert MTB/RIF ULTRA Detection Cycle Threshold.                           | Numeric       | LONG   |
| RE SPIROMETRY | REFVC            | Spirometry Forced Vital Capacity Actual value.                               | Numeric       | LONG   |

RESP30X-EBA: Statistical Analysis Plan22 JUL 2024

|               |            |  |         |      |
|---------------|------------|--|---------|------|
| RE SPIROMETRY | REFVC1     | Forced Expiratory Volume in 1 Second Actual value. | Numeric | LONG |
| RE SPIROMETRY | REFEV1_FVC | Modified Tiffeneau-Pinelli index Actual value.     | Numeric | LONG |
| CV SPMET      | CVSPMET    | SpMet Measurement Highest value.                   | Numeric | LONG |
| LB SAFETY     | LBHGB      | Haemoglobin in Blood Plasma.                       | Numeric | LONG |
| LB SAFETY     | LBBASOA    | Basophils Absolute (ABS) in Blood Plasma.          | Numeric | LONG |
| LB SAFETY     | LBEOSA     | Eosinophils Absolute (ABS) in Blood Plasma.        | Numeric | LONG |
| LB SAFETY     | LBIGA      | Imm Granulocyte Absolute (ABS) in Blood Plasma.    | Numeric | LONG |
| LB SAFETY     | LBLYMPHA   | Lymphocytes Absolute (ABS) in Blood Plasma.        | Numeric | LONG |
| LB SAFETY     | LBMONOA    | Monocytes Absolute (ABS) in Blood Plasma.          | Numeric | LONG |
| LB SAFETY     | LBNEUTA    | Neutrophils Absolute (ABS) in Blood Plasma.        | Numeric | LONG |
| LB SAFETY     | LBWBC      | White cell count in Blood Plasma.                  | Numeric | LONG |

**7.2 Analysis Software/Statistical Packages**

All study analysis datasets will be generated using SAS version 9.4. SAS version 9.4 will also be used for the Demography, Safety and Tolerability analysis. The R software version 4.3.1 or above will be used for EBA analysis and for safety figures and statistical models. SAS version 9.4 will be used to validate models to ensure consistent estimates from R software version. If updated versions of the above software become available these may be used and will be detailed in the Clinical Study Report.

**7.3 Changes in the Conduct of the Study or Planned Analysis**

Any deviations from the planned analysis will be provided and documented in the Statistical Reports and CSR (including Demographics, Safety and EBA). Information from these analyses will be combined into the Clinical Study Report.

**9 Interim Analysis for Safety and EBA**

The objective of stage 1 is to determine the EBA of inhaled RESP301, to inform ongoing development. When stage 1 is completed, recruitment will be paused, and an interim review will be conducted by a Trial Steering Committee (TSC) on the Safety and EBA. This will be detailed

RESP30X-EBA: Statistical Analysis Plan

22 JUL 2024

in the Trial Steering Committee Charter.

In order to progress to Stage 2, the following minimum should be met:

- RESP301 tds active treatment arm EBATTP(0-14): the predicted rate of change in the TTP in sputum over the period day 0 to 14 must be statistically different from zero at the 5 % level (demonstrating acceptable EBA to continue to Stage 2).
- $\leq 50\%$  of the participants experienced a grade 3 or higher AE.

A protocol amendment will be considered if the following safety and tolerability criteria are met:

- $\geq 25\%$  of the participants experienced a grade 2 or higher AE of any description considered probably or definitely related to IP.
- $\geq 20\%$  of the participants experienced a grade 3 or higher AE reflecting intolerance to IMP (gastrointestinal: diarrhoea, nausea, or dyspepsia; respiratory: bronchospasm).

The safety, tolerability, and EBA interim analysis will be conducted as described in Sections 10.1, 10.2, and 10.3 of this SAP respectively.

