#### Mono-Linear and Mono-Exponential Model For TTP

##### 1) Logarithmic function:

$$TTP = e^{\alpha_{\log}} \cdot \log_{10}(t) + A_{\log}$$

The model includes one intercept defined by A and one slope defined by  $\alpha$ .

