##### 2) Exponential decay upwards function:

$$TTP = A_{\exp} + B_{\exp} \cdot (1 - e^{\alpha_{\exp} \cdot t})$$

The model includes one intercept defined by A, one asymptote defined as B, and one slope defined by  $\alpha$ .

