## 10.3.2 Stochastic model (Random Effects)

### 1. Inter-individual variability

During the course of the model development, the Inter-individual (IIV) parameters will be tested on the structural parameters of the EBA models. Inter-individual parameters will be included in an exponential manner to ensure that the individual EBA parameters have a lower bound of zero:

$$P_i = \text{TVP} \cdot e^{\eta}$$

where TVP is the typical (Expected) value of the parameter P,  $P_i$  is the individual value of the parameter and  $\eta$  is a normally distributed random variable with mean 0 and standard deviation  $\sigma$ . Not all parameters need to be associated with IIV.

If the distributions of the  $\eta$ s are markedly non-normal, transformations of  $\eta$ s may be considered. Terms to describe correlations between  $\eta$ s will also be considered if indicated by the data. Initially, IIV should be added to the baseline only. IIV in other parameters should be explored after the treatment effect evaluation.

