### **10.3.6 Model discrimination**

The discrimination between models will mainly be made based on the inspection of graphical diagnostics and changes in the objective function value (OFV) and Akaike information criterion (AIC). The differences in OFVs are nominally  $\chi^2$  distributed and a difference of -3.64 corresponding to approximately a p-value of  $< 0.05$  for one degree of freedom, provided that the models are hierarchical. Preferably this should also demonstrate improvements in the graphical diagnostics and not lead to a high ( $>1000$ ) conditional number.

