### **10.3.8 Final model**

A final model should provide a good description of the observed data, not have any important trends in the relevant GOF diagnostics, have a successful termination of the covariance step and preferably have a condition number less than 1000. Should a model be accepted as final without these criteria being met, it will be discussed and justified in the report.

There will be one final model for each of the endpoints.

Based on the final EBA models for TTP and CFU, mean bactericidal activity per treatment arm will be expressed as the daily change in TTP and CFU from day 0 to day 14. If required, periods from 0 to 2 days, 0 to 7 days, 7-14 days, or any other period will be predicted or calculated as well as the 95% Bayesian credibility interval using only the patient data included in the study. Clinical trial simulations ( $n= 1000$ ) will be used to predict mean (95% prediction interval) bactericidal activity for different treatment arms and different characteristics depending on the covariates included in the final models.

Early bactericidal activity data definition table (DDT): A separate data specification table will be created for EBA. The dataset should be in excel csv format. A readme file describing the dataset column names should be created with an example for 1 participant.

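### The Stage 1 go rule in SAP 9 names no direction and no test, and the TTP functions printed in SAP 10.3.1 cannot support a test of zero slope as written

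*SAP*

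**What the plan says.** SAP section 9 sets two minimum conditions for Stage 2. One is a limit on grade 3 or higher adverse events. The other is that the model-predicted TTP rate over days 0 to 14 in the RESP301 tds arm "must be statistically different from zero at the 5 % level (demonstrating acceptable EBA to continue to Stage 2". For the method, the section refers to SAP 10.1 to 10.3.

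SAP 10.3 contains these relevant pieces:

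- **10.3.1, TTP function 1 (logarithmic):** "TTP = e^{\alpha_{\log}} \cdot \log_{10}(t) + A_{\log".
- **10.3.1, TTP function 2 (titled as an upward function):** "TTP = A_{\exp} + B_{\exp} \cdot (1 - e^{\alpha_{\exp} \cdot t".
- **10.3.2:** random effects enter exponentially "to ensure that the individual EBA parameters have a lower bound of zero".
- **10.3.6:** for comparing models, "a difference of -3.64 corresponding to approximately a p-value of" less than 0.05 on one degree of freedom.
- **10.3.8:** daily change from day 0 to day 14, with other periods if required, "as well as the 95% Bayesian credibility interval using only the patient data included in the study"; also, simulations "will be used to predict mean (95% prediction interval) bactericidal activity for different treatment arms".

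None of these is tied to the gate. The heading above function 1 mentions a mono-linear model, and protocol 1.2 allows linear functions, but SAP 10.3.1 prints no linear formula for TTP. SAP 4.3 describes the study as having no hypothesis testing.

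Both documents suspect that nitric oxide left in sputum may kill bacilli in the sample itself (protocol 3.2 and 3.3.3, SAP 3). A drug-free Day 15 sample is taken for that reason, and SAP 11.3 tabulates EBA over 0-15 and 14-15.

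**The concern.** This is the only 5% significance decision before Stage 2. A reader of the visible SAP cannot tell which statistic is compared with what, in which direction, or from which model. The candidate tools in 10.3 do not agree with one another: on the same inactive data one can pass by construction and another about 2.5% of the time. SAP 10.3 also leaves fuller model definitions to the later EBA report, so the choice could be made after the data are seen. The false-go rate is therefore not fixed by the plan.

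**Working it through.** **1. The printed cutoff.** Chi-square tail on 1 df: P(X > 3.64) = 0.0564 and P(X > 3.84) = 0.0500. The figure printed for p < 0.05 should be 3.84.

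**2. TTP function 1.** The slope on log10(t) is e^alpha.

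- At t = 0, log10(t) is minus infinity, so the function has no day 0 value, although the gate runs from day 0.
- The day 1 to day 14 change is e^alpha × log10(14) = e^alpha × 1.146. For alpha = -5, 0 and 3 this is +0.008 h, +1.15 h and +23.0 h. It is never zero or negative.
- Zero slope needs alpha at minus infinity. A test of alpha = 0 would test a slope of 1, not of 0.

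**3. TTP function 2.** The change from day 0 to day 14 is B(1 - e^(14·alpha)). With illustrative values B = 50 h and alpha = 0.1:

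- as printed: 50 × (1 - e^1.4) = -153 h;
- with a minus sign in the exponent: 50 × (1 - e^-1.4) = +37.7 h.

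With B and alpha both positive, the printed form can only fall, contrary to its title.

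**4. Pass rate for an inactive drug, by choice of test.**

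| Test | Pass rate |
|---|---|
| Credible or percentile interval on e^alpha (function 1) | 100%, by construction |
| Wald interval exp(alpha ± 1.96 SE) (function 1) | about 50% (whenever the fitted slope is positive) |
| Likelihood ratio, slope held non-negative | 2.5% at 3.84, 2.8% at 3.64 (asymptotic) |
| The same at 3.64, simulated, n = 15 to 12 | 3.5% to 3.8% |
| Likelihood ratio at 3.64, free slope, simulated, n = 15 to 12 | 7.0% to 7.6% |
| Two-sided 5% t test, free slope | 5.0%, half of it downward |
| Free slope, two-sided 95% interval wholly above zero | 2.5% |

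The simulations used 20,000 runs of per-patient slopes on log10(t), days 1 to 14. They assumed a residual SD of 20 h and a between-patient slope SD of 1 h/day, neither of which is in the documents.

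**5. Supporting check on residual nitric oxide (illustration only).** Suppose a constant shift in TTP on Days 1 to 14 with no killing. Fit a straight line per patient, take n = 15, and require the interval to lie above zero. Assume a residual SD of 20 to 40 h and a slope SD of 0 to 1 h/day. The fitted slope per hour of shift is 0.0403 with two baseline records at t = 0 (Sxx = 325.94), and 7/280 = 0.025 with one. SAP 7.1 defines the baseline variable as "Baseline bacterial load. (average TTP on days -2 and -1").

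| Assumed shift | Two baseline records | One averaged baseline |
|---|---|---|
| 10 h | 8.7% to 25.9% | 5.5% to 12.1% |
| 20 h | 22.3% to 74.5% | 10.8% to 35.2% |

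With no shift the rate is 2.5%. A slope fitted on Days 1 to 14 alone has coefficient 0 for a constant shift and stays at 2.5%. For the same reason, function 1 fitted without day 0 takes up none of a constant shift.

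**The case against.** **A test may exist elsewhere.** The progression criteria in protocol 8.3 and the analysis method in 8.4.1 are redacted, and the Steering Committee Charter is not supplied. This stands: the point is limited to the visible text. A reader might infer that the trial has no gate test at all; the documents do not support that.

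**The 100% figure is a corner case.** It needs function 1 as the final model and a credible or percentile interval as the test. SAP 10.3.1 leaves other functions open. SAP 10.3.5 and 10.3.8 ask for relative standard errors, visual predictive checks, a good description of the data and a successful covariance step, with exceptions justified. These make a degenerate fit less likely to go unnoticed. So the inference that the gate passes whatever the data is too strong. The checks are not error control, however, and do not fix the false-go rate.

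**The zero bound in SAP 10.3.2 does not settle the sign.** The exponential form keeps the sign of the typical value, whatever that is, and random effects are optional by parameter. That stands; the bound does not by itself force the population slope upward. The missing minus sign in function 2 may be a misprint or a loss in text conversion, since the title makes the intent clear. It still needs confirming.

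**Direction is implied.** The reference to acceptable EBA, with the SAP's definition of EBA as killing, points upward. True, but the criterion itself says only that the rate differs from zero.

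**Day 15 is already covered.** The 0-15 and 14-15 tables are planned and the EBA analysis runs at the interim, so the committee probably sees them. It is tempting to infer that the go decision ignores residual nitric oxide, or that Day 15 should be a gate. Neither follows: the size of any shift is unknown, the collection pause and water rinse limit it, and the rates above show a mechanism, not a magnitude.

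**Conclusion.** The point holds for the visible SAP. The gate names no direction and no test. Function 1 is undefined at day 0 and cannot represent a zero or negative slope; function 2 falls as printed for positive parameters; and 3.64 is not the 5% cutoff. Depending on the tool picked, the false-go rate runs from about 2.5% to 100%, the upper end only in the specific combination described. With a free slope and a two-sided 5% test it is 5%, of which 2.5% is in the wrong direction. These findings rest on the printed formulas and the chi-square distribution; only the simulated rates and the nitric oxide figures depend on assumed variability. It should be fixed before the interim. It does not show that the trial would proceed wrongly, because a steering committee decides above this minimum.

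**What to change.** 1. Replace the SAP 9 activity bullet with: *the lower limit of the two-sided 95% confidence interval for the model-predicted mean TTP change from day 0 to day 14 in the RESP301 tds arm is above 0.* Require a model that is defined at day 0 (for example linear in t, or in log10(t + 1)), has a population slope free to take either sign, and includes between-participant variability in slope.
2. Correct the sign of the exponent in TTP function 2.
3. Change 3.64 to 3.84 in SAP 10.3.6.
4. As information and not as a gate, show beside the result the baseline-to-Day-15 change with its 95% interval and a Day 1 to 14 slope.
5. As a separate consistency point, reconcile the sputum-collection pause: 1 hour after any overlapping dose in protocol 1.3 footnote M, 30 minutes after the evening dose in SAP Table 5 footnote I.

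The cost is SAP wording and one extra fit; the Day 15 samples and tables are already planned. The supporting estimates are less precise: against the 0-14 slope, the standard error per day is 9% to 20% larger for Day 1 to 14 and 26% to 47% larger for baseline to Day 15. For a true linear change of 11 h (the SAP 4.3 planning figure, used only as a scale), with n = 15 and the straight-line assumptions above, power is 17% to 57% and 13% to 41%, against 21% to 72% for 0-14. That is why they should inform rather than gate. The Day 1 to 14 slope also discards killing before the Day 1 sample and is protected only against a constant shift; the Day 15 change is clean only if no nitric oxide remains by then. Because the final model is still chosen from the data, 2.5% is a nominal false-go rate, not an exact one.

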2.2.3.1. RESP301 development program

- [REDACTED]
- [REDACTED]
- [REDACTED]
- [REDACTED]

Table 8: RESP301 Clinical Studies

Study	Status	Title	No of participants receiving at least 1 dose of RESP301	Comment
RESP301-005 (CORVIS)	Completed	Phase 2 study, entitled, "Community patients at Risk of Viral Infections including SARS-CoV-2".	39	Single ascending dose study
RESP301-003 (NOMab)	Ongoing	Phase II, open label single centre study assessing the efficacy, safety and tolerability of RESP301, a nebulized nitric oxide generating solution, in patients with M. abscessus -pulmonary disease	5	
RESP301-007 (PROTECT-Surg)	Ongoing	A Phase 2, Platform, Randomized Clinical Study entitled, "Preventing pulmonary complications in surgical subjects at risk of COVID-19".	79	
RESP301-002 - NOCOv2	Terminated early	An open-label, adaptive randomized, controlled multicentre study to evaluate the efficacy and safety of RESP301+SOC vs SOC in hospitalized participants with COVID-19 WHO grade 3&4.	14	Early terminated due to changes in the standard of care during the study and limited patient availability
RESP301-006 (PREVENT)	Terminated early	Phase 2/3 study, entitled, "Prevent Viral Exposure and Transmission study: a SARS-CoV-2 PEP Study"	0	Whilst approved by the Ethics Committee and Regulatory Authority, was never initiated due to lower than anticipated numbers of patients meeting the eligibility criteria

As of 30 March 2023, a total of 175 AEs have been reported in 51 patients across the RESP301 development programme, of which 60 were deemed highly probably related to RESP301. Of note 52 (87%) of these AEs were reported in RESP301-005 (CORVIS study) in patients with COPD/Bronchiectasis with cough being the most frequently reported AE in this group.

RESP301 has been generally well tolerated, but there appears to be a small sub-population of patients, notably Chronic Obstructive Pulmonary Disease (COPD) patients with airway hyperresponsiveness complicated by very poor underlying respiratory function (FEV1 less than 30% of predicted) who may be at increased risk of AEs (specifically bronchoconstriction). This appears to be rapidly reversed with short acting bronchodilators (SABA) and may be prevented by pre-dosing with a SABA, as demonstrated in the Single Ascending Dose portion of the CORVIS study. Given this, patients with a FEV1 of less than 40% prior to dosing with the IMP will be excluded from this study.

In addition:

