- is a medically important event.

Note: Medical and scientific judgment should be exercised in deciding whether an AE is a medically important event that may not be immediately life-threatening or result in death or hospitalization but may jeopardize the participant or may require medical or surgical intervention to prevent one of the outcomes listed above. Examples of such events are intensive treatment in an emergency room or at home for allergic bronchospasm, blood dyscrasias or convulsions that do not result in hospitalization, or the development of drug dependency or drug abuse. A “suspected transmission of infectious agent by a medicinal product” is also considered a serious adverse event under the SAE criterion “Other medically important condition”.

Adverse Drug Reaction (ADR)

An ADR is defined as a response to a medicinal product which is noxious and unintended at any dose and that is considered causally related (possible, probable, or certain) to an investigational medicinal product. A serious ADR (SADR) is an ADR which meets the serious criteria.

Unlisted (Unexpected) Adverse Event

An adverse reaction, the nature or severity of which is not consistent with the applicable product information (e.g., Investigator's Brochure for an unapproved investigational product or package insert/summary of product characteristics for an approved product). Expectedness is assessed by the sponsor/sponsor's delegate.

Attribution/Causality

The definitions for rating attribution/causality will be as described in Table 21.

Table 21: Adverse Events Attribution/Causality Ratings

Relatedness Rating	Definition
Not Related	An adverse event, which is not related to the use of the drug.

Relatedness Rating	Definition
Unlikely	An adverse event for which an alternative explanation is more likely, e.g., concomitant drug(s) or concomitant disease(s), and/or the relationship in time suggests that a causal relationship is unlikely.
Possible	An adverse event, which might be due to the use of the drug. An alternative explanation, e.g., concomitant drug(s) or concomitant disease(s), is inconclusive. The relationship in time is reasonable; therefore, the causal relationship cannot be excluded.

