Probable	An adverse event, which might be due to the use of the drug. The relationship in time is suggestive, e.g., suspicion strengthened by onset of symptoms associated with initiation of drug and/or improvement of symptoms when stopping drug. An alternative explanation is less likely, e.g., concomitant drug(s) or concomitant disease(s).
Certain	An adverse event, which is listed as a possible adverse reaction and cannot be reasonably explained by an alternative explanation, e.g., concomitant drug(s) or concomitant disease(s).

Severity

Severity rating is to be made per the CTCAE Toxicity Table Version 5 dated 27 November 2017 (Appendix 1). For abnormalities NOT found in the toxicity tables, the scale described in Table 22 is to be used to estimate grade of severity.

Table 22: Adverse Event Severity Ratings

Grade	Severity Rating	Definition
Grade 1	Mild	Transient or mild discomfort (< 48 hours); no medical intervention/therapy required.
Grade 2	Moderate	Mild to moderate limitation in activity - some assistance may be needed; no or minimal medical intervention/ therapy required.
Grade 3	Severe	Marked limitation in activity, some assistance usually required; medical intervention/therapy required, hospitalizations possible.
Grade 4	Potentially Life-threatening	Extreme limitation in activity, significant assistance required; significant medical intervention/therapy required, hospitalization or hospice care probable.

Action taken and outcome

The investigator will record the actions taken with the IMP for each AE using the descriptions in Table 23.

Table 23: Adverse Events Action taken with Investigational Medicinal Product

Action Taken	Definition
IMP withdrawn	Participant is permanently withdrawn from the IMP
IMP interrupted	IMP is temporarily withdrawn
IMP unchanged	No action is taken regarding the IMP
Unknown	It is not known what action was taken with the IMP

Action Taken	Definition
Not Applicable	The IMP treatment has been completed prior to reaction /event, or the participant has died
IMP: Investigational Medicinal Product	

The investigator will record the other actions taken, the outcome and the occurrence for each AE using the following descriptions:

Other Action Taken

- none
- medication given
- hospitalisation or prolongation of hospitalisation
- therapeutic or diagnostic procedure.

Outcome

- recovered / resolved
- recovering / resolving
- not recovered / not resolved
- recovered / resolved with sequelae
- fatal
- unknown.

Occurrence

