7.6. Disease under Study

Symptoms of the disease under study (pulmonary TB) experienced by the participant while on the study will be assessed by the investigator. If the symptom has:

- worsened while the participant is in the study; and
- the investigator assesses it as clinically significant

it will be recorded as an adverse event. If it does not meet these criteria, it will not be recorded as an AE and will be noted in the participant's source documentation. All TB related symptoms that meet SAE criteria will be recorded and reported as a SAE.

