| AE Criteria   |                  |            |           |           |      |
| Grade 3 or higher AEs   |                  |            |           |           |      |
| Yes   |                  |            |           |           |      |
| No  |                  |            |           |           |      |
| Moderate (grade 2) or higher grade toxicity (CTCAE V5.0), that is probably or definitely related to IP  |                  |            |           |           |      |
| Yes   |                  |            |           |           |      |
| No  |                  |            |           |           |      |
| Grade 3 or higher AEs (Gastrointestinal: diarrhoea, nausea, or dyspepsia; Respiratory: bronchospasm) that are at least possibly related to IP |                  |            |           |           |      |
| Yes   |                  |            |           |           |      |
| No  |                  |            |           |           |      |

RESP30X-EBA: Statistical Analysis Plan22 JUL 2024Table 14.4.1: Positive and non-positive data in the dataset for CFU status at the different timepoints  
EBA

| Sample status             | All Participants |       | HRZE  |       | RESP301tds |       | RESP301qd |       | R |
|---------------------------|------------------|-------|-------|-------|------------|-------|-----------|-------|---|
|                           | Rep 1            | Rep 2 | Rep 1 | Rep 2 | Rep 1      | Rep 2 | Rep 1     | Rep 2 |   |
| Day -1                    |                  |       |       |       |            |       |           |       |   |
| Contaminated              |                  |       |       |       |            |       |           |       |   |
| No Growth/Negative        |                  |       |       |       |            |       |           |       |   |
| No Result                 |                  |       |       |       |            |       |           |       |   |
| No Done                   |                  |       |       |       |            |       |           |       |   |
| Positive                  |                  |       |       |       |            |       |           |       |   |
| Repeat for each Study Day |                  |       |       |       |            |       |           |       |   |

RESP30X-EBA: Statistical Analysis Plan22 JUL 2024Table 14.4.4: Summary statistics of baseline discrete covariates for the treatment arms  
EBA

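### The 20% intolerance trigger for a nebulised drug has bronchospasm as its only airway term, so severe related cough, or dyspnoea or wheeze recorded without a diagnosis, is not counted

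*SAP*

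**What the plan says.** SAP 9 sets two minimum conditions for moving to Stage 2. One of them is that no more than 50% of participants have a Grade 3 or higher AE, whatever its term or cause. It then gives two criteria under which an amendment will be considered:

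- at least 25% of participants "experienced a grade 2 or higher AE of any description considered probably or definitely related to IP";
- at least 20% with a "grade 3 or higher AE reflecting intolerance to IMP (gastrointestinal: diarrhoea, nausea, or dyspepsia; respiratory: bronchospasm").

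The second list has no wording that would make it a set of examples. The third row of Table 14.3.7, which reports this criterion, reads "Grade 3 or higher AEs (Gastrointestinal: diarrhoea, nausea, or dyspepsia; Respiratory: bronchospasm) that are at least possibly related to IP". It has the same terms plus a relatedness condition that SAP 9 does not state. The SAP gives no synonym list or MedDRA grouping.

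Protocol 2.2.3.1 describes the airway effects of RESP301 in other words. It identifies a small group, notably COPD patients with hyperresponsive airways and very poor lung function, "who may be at increased risk of AEs (specifically bronchoconstriction"). It also places 52 of the 60 highly probably related AEs in COPD/bronchiectasis patients of one completed study, "with cough being the most frequently reported AE in this group".

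Protocol 7.2 asks for a diagnosis where one can be made. Individual signs and symptoms are recorded as separate AEs only where it cannot.

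**The concern.** The 20% criterion is the one written to detect intolerance, and the product is inhaled. It has three gut terms and one airway term. Cough, the airway event that the protocol reports most often in the group with most of the related events, is not on the list. Applied literally, the third row of Table 14.3.7 would show No for a participant with a severe, drug-related cough.

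The 25% criterion accepts any term, but it leaves out events rated Possible. That rating is plausible in pulmonary TB, because Table 21 of the protocol uses it when "An alternative explanation, e.g., concomitant drug(s) or concomitant disease(s), is inconclusive". At stake is whether a stated safety rule prompts the discussion it was written to prompt.

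**Working it through.** The plan gives no operating characteristics for these rules, so there is no figure to reproduce. The check is rule arithmetic.

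**Inputs.** The thresholds of 20%, 25% and 50% come from SAP 9. The planned size of the RESP301 tds arm is 15 (SAP 4.3). Table 14.3.7 uses the Safety Population, meaning all randomised and dosed participants (SAP 6), and SAP 10.2.2 summarises it per treatment group. So n can differ from 15 if participants are not dosed or are replaced.

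**Formula.** For each n, find the smallest count k with k/n ≥ 0.20, with k/n ≥ 0.25, and with k/n > 0.50.

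| n | 20% trigger | 25% trigger | 50% limit exceeded |
|---|---|---|---|
| 12 | 3 (25.0%) | 3 (25.0%) | 7 (58.3%) |
| 13 | 3 (23.1%) | 4 (30.8%) | 7 (53.8%) |
| 14 | 3 (21.4%) | 4 (28.6%) | 8 (57.1%) |
| 15 | 3 (20.0%) | 4 (26.7%) | 8 (53.3%) |
| 16 | 4 (25.0%) | 4 (25.0%) | 9 (56.25%) |

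**Reference case, n = 15.** Three participants with related Grade 3+ bronchospasm meet the 20% trigger, since 3/15 = 20.0%.

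**Unlisted term, rated only Possible, n = 15.** Suppose 3 to 7 participants have Grade 3+ cough, or dyspnoea or wheeze without a diagnosis, and no other events count.

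- The 20% trigger is not met, because the term is not listed.
- The 25% trigger is not met, because the rating is too low.
- The 50% limit is not exceeded: 7/15 = 46.7%.

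Such events count toward neither amendment criterion at any n.

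**Unlisted term, rated probable or definite, n = 15.** With exactly 3 participants, the 20% trigger is not met, and 3/15 is below 25%. One more participant with any probably or definitely related Grade 2+ event gives 4/15 = 26.7% and meets the 25% trigger. This gap depends on n. It exists at 13, 14 and 15, where the two triggers need 3 and 4 participants. It vanishes at 12 (both need 3) and at 16 (both need 4).

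**Denominator of 20.** If all 20 Stage 1 participants were used, the triggers would need 4 and 5 participants and the limit would allow 10. The pattern is the same.

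**Illustration on assumed rates only.** The documents give no expected rate of severe airway reactions. Suppose the true rate of related Grade 3+ airway reactions is 10%, 20%, 30% or 40%, and n = 15. If every term counted, the exact binomial chance of at least 3 would be 0.18, 0.60, 0.87 and 0.97. If half of the reactions were recorded as bronchospasm and only those counted, it would be 0.04, 0.18, 0.40 and 0.60. Neither the rates nor the share can be taken from the documents.

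**The case against.** **Recording by diagnosis.** A reader might infer that bronchoconstriction and wheeze are shut out of the trigger. The documents do not support that. Under Protocol 7.2 a diagnosis is recorded where possible, and under 5.3.3 trained staff stay with the participant during nebulisation. An acute severe wheeze would often be recorded as bronchospasm. Bronchoconstriction that reverses rapidly with a short-acting bronchodilator, as 2.2.3.1 describes, is plausibly read the same way. This stands. The firm gap is cough, plus dyspnoea or wheeze for which no diagnosis is made.

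**The cough evidence.** It comes from COPD/bronchiectasis patients and has no stated severity. This trial excludes FEV1 below 40%, starts tds dosing with two half doses and calls for a bronchodilator before each Day 1 dose. Nothing in the documents reports a Grade 3 or higher cough. A reader might infer that such events are to be expected here; the documents do not show that.

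**The 25% rule as backstop.** Table 21 allows a Probable rating on "suspicion strengthened by onset of symptoms associated with initiation of drug and/or improvement of symptoms when stopping drug", which suits an acute reaction to inhalation. This stands in part: it narrows the gap but leaves the Possible events uncounted.

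**Nothing is blocked.** The trigger only leads to an amendment being considered. The investigator evaluates every Grade 3 or 4 event (Protocol 7.10.4), a Safety Review Committee meets on pre-determined events (7.11), and the study can be halted for unacceptable risk (SAP 4.9). This limits the consequence. It does not complete the list.

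**Specificity.** Cough and dyspnoea are TB symptoms, and leaving them out keeps the trigger specific. This is a fair trade-off and is the real cost of the change.

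**Relatedness wording.** The SAP 9 text already implies attribution to the study drug. That is reasonable, so the mismatch with Table 14.3.7 is minor.

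**Conclusion.** The point holds as a gap in one pre-specified criterion, and it is an optional improvement. The size is the set of count patterns shown for n = 15. Each pattern assumes that no other participant has a qualifying event and that the list is applied as written. No probability of a missed trigger can be derived from the documents.

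A reader might go further and conclude that severe airway toxicity could pass into Stage 2 unseen. The documents do not support this. SAP 9 has the interim safety analysis follow 10.2, and the tables planned in SAP 11.2 include Table 14.3.1.7.4, which shows all treatment-emergent events by preferred term, maximum severity and relationship. What is missing is the prompt from the rule, not the data.

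The record is also incomplete. The criteria in Protocol 8.3 and the risk list in 2.4 are redacted, and the committee charters are not in the documents. A wider definition could exist there.

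**What to change.** In SAP 9, restate the 20% criterion so that it counts Grade 3 or higher AEs at least possibly related to IMP. Keep the three gastrointestinal terms, and make the respiratory entry bronchospasm (stated to include bronchoconstriction and wheeze), cough or dyspnoea. Use the same respiratory list in the third row of Table 14.3.7, which already has the relatedness condition. Count each participant once.

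This costs one SAP sentence and one row label before the interim tables are run, and it needs no new data. The downside is that some TB-related worsening of cough or dyspnoea rated Possible may be counted. The Grade 3 threshold limits this, and so does Protocol 7.6, under which a TB symptom must have worsened and be clinically significant: "If it does not meet these criteria, it will not be recorded as an AE". A false alarm leads only to a discussion of an amendment.
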